#### **Risks Associated with Blood Drawing and IV Line Insertion**

At the screening visit, a routine venipuncture will be performed for screening laboratory studies. On the PET scan day(s), up to two venous catheters will be inserted for administration of the radiotracer and for blood draws.

Drawing blood and inserting an intravenous line (IV) into an arm vein are safe and standard medical procedures. Sometimes a bruise will occur at the puncture site and rarely a blood clot or infection will occur in the vein. Certain individuals may feel light-headed during venipuncture.

The volume of blood collected during this study will be up to 32 tablespoons. Blood samples will be drawn for routine labs and drug screening; measurement of radiopharmaceutical parent and metabolites, for analysis of plasma drug levels, serum estrogen, progesterone, and follicle stimulating hormone levels. This is not expected to have any serious negative effects on a study participant.

#### **Risks Associated with Radiation**

The Yale University Radioactive Drug Research Committee (YU RDRC) will review the use of radiation in this research study, and no subjects will be scanned until approval is obtained. This research study involves exposure to radiation from [C]ABP688 and/or [F]FPEB . This radiation exposure is not necessary for medical care and is for research purposes only.

The maximum amount of radiation an individual subject may receive in this study would be if they participated in both Aim 1 and Aim 2 of this study. This participation would involve two injections of  $\leq 20$  mCi of [C]ABP688 (0.2360 rem each), two injections of  $\leq 5$  mCi of [F]FPEB (0.312 rem each), plus a small amount of radiation from the transmission scans of the brain.

Although each organ will receive a different dose, the maximum amount of radiation exposure subjects could receive from this study is equal to an effective dose of **1.102 rem** for a total of up to 40 mCi of [C]ABP688 and 10 mCi [F]FPEB from four total injections and 4 transmission scans (.0014rem each). This calculated value is used to relate the dose received by each organ to a single value. Subjects may get an additional injection of either radiotracer if needed due to scan failure after injection, this would bring the total possible rem to **1.652 Rem** from 3 injections of each tracer and 6 transmission scans.

Subjects may participate in more than one aim, not to exceed **1.652 Rem** total and not to exceed 3 injections of either tracer total.

The amount of radiation subjects will receive in this study is below the dose guidelines established by the FDA and monitored by **the Yale University Radioactive Research Committee** for research subjects. This guideline sets an effective dose limit of 5 rem per year.

Adverse effects of the radiopharmaceuticals in this study have not been reported. However, the possibility exists for a rare reaction to any of the substances or procedures to which a subject is exposed.

#### **Risks Associated with MRI**

MR carries a risk for subjects who are claustrophobic or have pacemakers, metal pieces, aneurysm clips, large colored tattoos, or any other contraindications for MR.

Magnetic resonance imaging (MRI) is a technique that uses magnetism and radio waves, not x- rays, to take pictures and measure chemicals of various parts of the body. The United States Food and Drug Administration (FDA) has set guidelines for magnet strength and exposure to radio waves, and we carefully observe those guidelines.

Subjects will be watched closely throughout the MR study. Some people may feel uncomfortable or anxious. If this happens, the subject may ask to stop the study at any time and we will take them out of the MRI scanner. On rare occasions, some people might feel dizzy, get an upset stomach, have a metallic taste or feel tingling sensations or muscle twitches. These sensations usually go away quickly but we will ask subjects to tell the research staff if they have any of these symptoms.

There are some risks with an MRI study for certain people. If subjects have a pacemaker or some metal objects inside their body, they may not be in this study because the strong magnets in the MRI scanner might harm them. Another risk is the possibility of metal objects being pulled into the magnet and hitting a subject. To reduce this risk we require that all people involved with the study remove all metal from their clothing and all metal objects from their pockets. We also ask all people involved with the study to walk through a detector designed to detect metal objects. It is important to know that no metal can be brought into the magnet room at any time. Also, once subjects are in the magnet, the door to the room will be closed so that no one from outside accidentally goes near the magnet.

We want subjects read and answer very carefully the questions on the MRI Safety Questionnaire related to your personal safety. We will be sure that subjects have read the MRI Safety Questionnaire and tell us any information they think might be important.

This MRI study is for research purposes only and is not in any way a clinical examination.

The scans performed in this study are not designed to find abnormalities. **The primary investigator, the lab, the MRI technologist, and the Magnetic Resonance Research Center are not qualified to interpret the MR scans and are not responsible for providing a diagnostic evaluation of the images.** If a worrisome finding is seen on a subject's scan, a radiologist will be asked to review the relevant images. Based on his or her recommendation (if any), the primary investigator or consulting physician will contact the subject, inform them of the finding, and recommend that they seek medical advice as a precautionary measure. The decision for additional examination or treatment would lie solely with the subject and your physician. **The investigators, the consulting physician, the Magnetic Resonance Research Center, and Yale University are not responsible for any examination or treatment that a subject receives based on these findings. The images collected in this study are not a clinical MRI exam and for that reason, they will not be made available for diagnostic purposes.**

#### **Risks Associated with Drug Use and Suicidal/Homicidal Behavior**

Participants will be asked about current or past use of illicit "street" drugs and urine drug screens will be performed at the initial intake appointment to rule out substance abuse that is not relevant to the study. Participants currently using drugs or who have a history of using drugs may not be eligible to participate. Suicidal thoughts and behaviors will also be assessed as this is a prevalent comorbidity in subjects with mood and substance disorders. Any reports of homicidal or significant suicidal tendencies will be immediately directed to treatment for this condition; and appropriate authorities will be notified.

#### **Risks Associated with Unanticipated Events**

The subject's health and safety will always be the primary concern of the doctors and staff performing the study. In the event of an unanticipated event, all necessary medical action will be taken. Medication might be administered as needed, per the Yale PET Center standard operating procedure for medical emergencies, in order to treat any unanticipated events/complications.

#### **Risks Associated with Allergic Reactions**

All drugs have a potential risk of an allergic reaction, which if not treated promptly, could become life threatening.

11. **Minimizing Risks:** Describe the manner in which the above-mentioned risks will be minimized.

#### **Risks Associated with Administration of Alcohol:**

Risks will be minimized by adhering to the recommended guidelines established by the National Advisory Council on Alcohol Abuse and Alcoholism – Recommended Council Guidelines on Ethyl Alcohol Administration in Human Experimentation – Revised May 2005. People for whom alcohol consumption is contraindicated will be excluded based on the screening process including interviews, physical exams, and laboratory findings.

To reduce the risk of nausea or gross impairment from acute alcohol consumption, we will enroll participants with recent (within the last three months) drinking experience consistent with the blood alcohol concentration targeted for this study. We will provide a light lunch prior to the alcohol session.

Personnel trained in the conduct of alcohol challenges will conduct the sessions. All participants will be under supervision to prevent possible accidents. Following the alcohol sessions, all subjects will remain the CNRU or HRU overnight to prevent the possibility that they might continue drinking after the session, thereby placing themselves at further risk of accidents.

Participants will be strongly encouraged to remain in the research setting until their breath alcohol level is below 0.02. If a participant should insist on leaving the research setting prematurely, they will first demonstrate capacity to make an informed decision. This will be done by assessing subject's ability to understand the risks of an early discharge, understanding the alternatives and benefits of following the set guidelines, assessing comparative and consequential reasoning, and understanding how their final decision was reached. Should a participant insist on withdrawing before BAC of 0.02, the CSSRS will also be administered to confirm the absence of symptoms. Should capacity to make this informed decision be demonstrated, we will provide transportation to their home. The consent form addresses this contingency under voluntary participation.

**Risks Associated with Use of an Arterial Catheter:**

Risks of radial artery cannulation are minimized by having the procedure performed by an experienced health care provider. The health care provider would be either a physician or an advanced practice registered nurse (APRN) with experience in critical care and placement of arterial catheters, as is the practice at Yale-New Haven Hospital. For an APRN to place the arterial line at the Yale PET Center, they must meet the following criteria:

- 1.) Be currently credentialed at Yale-New Haven Hospital or similar institute and
- 2.) Perform 3 arterial line procedures supervised by a currently privileged PET Center physician

The 3 supervised arterial line placements will be documented and signed off by both the APRN and supervising physician. The completed document must be on file at the Yale PET Center prior to an APRN performing any arterial line catheterizations independently.

Pain is minimized with the use of local anesthesia. Infection is avoided by adequate cleansing of the skin before intravascular line insertion. After arterial catheter removal, bleeding is prevented by direct pressure applied to the site for a minimum of 15 minutes followed by a pressure dressing (coban) that should be kept clean and dry until evening. Subjects will have their hand and finger blood supply examined after arterial cannulation throughout the study, and again following catheter removal. Also, subjects will be asked to abstain from using aspirin and other NSAIDS for 7-10 days prior to arterial line insertion and 7-10 days following arterial line removal. Subjects will be provided a 24-hour emergency physician contact number to call if they encounter pain, discoloration, numbness, tingling, coolness, hematoma, inflammation, or any other unusual symptoms in the wrist or hand, or fever, chills or drainage from the vascular puncture sites, following the procedure. In addition, if an emergency arises at the time of cannulation or scanning, 911 will be called, and the subject will be sent to the Emergency Department for evaluation and treatment. A nurse

will provide discharge instructions outlining general instructions in addition to post-arterial catheter precautions, problems to watch for, and procedures to follow should such problems occur.

**Risks Associated with Blood Drawing & IV Line Insertion:**

The risks of bruising, clotting, and infection will be minimized by having venipuncture performed by trained and experienced personnel using aseptic technique. To avoid injury due to fainting, the catheter will be inserted when the subjects are in a recumbent position. The blood draws during PET scanning sessions will be obtained from the already inserted catheter, to minimize discomfort. Subjects who have donated blood within 8 weeks of the present study will be excluded. Participants will be told that they should not give blood for at least 8 weeks.

**Risks Associated with Radiation:**

The dose of radiation will be submitted for approval to the Yale University Radioactive Drug Research Committee (YU RDRC). All scans will be done in the presence of medical supervision and trained staff in an institution specifically designed to support imaging studies. In the event of serious medical complications, the PET scan facilities have immediate access to or consultation with specialized medical units at the Yale-New Haven Hospital. Preparation of radiopharmaceuticals and performance of PET scans will be by radiochemists, physicians, and technologists of the Department of Diagnostic Radiology, Yale University School of Medicine. These professionals are qualified by training and experience in the safe use and handling of radiopharmaceuticals. Subjects will be asked about their previous radiation exposure and those who have had research exposure within the past year will be excluded if their cumulative annual exposure (including the present study) exceeds FDA limits. The information on the previous radiation exposure of study subjects will be notified to the study doctor.

No PET studies will be performed on pregnant or potentially pregnant women, as confirmed by pregnancy testing during evaluation and on each scan day before initiation of any scan procedures. If subjects are breastfeeding they will not be able to participate in this research study.

**Risks Associated with MRI Scanning**

To minimize risks, each subject will fill out the Yale Magnetic Resonance Research Center MRI Safety Questionnaire before the study. Only subjects who fulfill the criteria by this questionnaire will be eligible for the study. In addition, subjects will remove all metal (watch, hair pins, jewelry) and walk through the metal detector in the MRRC before entering the MRI room. If the subject has any metallic prostheses/implants they will be excluded from the study. If a subject becomes anxious during the scan they can request that the MRI scan be stopped.

**Risks Associated with Drug Use and Suicidal/Homicidal Behavior**

Effective screening will exclude all subjects who would be at greater risk for complications because of medical or psychiatric illnesses. Any subject with a prior suicide attempt or with active suicidal ideation at baseline as determined by psychiatric evaluation and C-SSRS, will be excluded from this study.

The subject's health and safety will always be the primary concern of the doctors and staff performing the study. In the event of an unexpected outcome, all necessary medical action will be taken.

**Risks Associated with Unanticipated Events**

Medication might be administered as needed, per the Yale PET Center standard operating procedure for medical emergencies, in order to treat complications

The subject's health and safety will always be the primary concern of the doctors and staff performing the study. In the event of an unexpected outcome, all necessary medical action will be taken.

12. **Data and Safety Monitoring Plan:** Include an appropriate Data and Safety Monitoring Plan (DSMP) based on the investigator's risk assessment stated below. (Note: the HIC will make the final determination of the risk to subjects.)

- a. What is the investigator's assessment of the overall risk level for subjects participating in this study? Greater than minimal Risk
- b. If children are involved, what is the investigator's assessment of the overall risk level for the children participating in this study? N/A
- c. Include an appropriate Data and Safety Monitoring Plan. Examples of DSMPs are available here <http://your.yale.edu/policies-procedures/forms/420-fr-01-data-and-safety-monitoring-plans-templates> for
  - i. Minimal risk
  - ii. Greater than minimal

**1. Personnel responsible for safety review and its frequency:**

The principal investigator, in collaboration with [name]., and [name]., will be responsible for monitoring the data, assuring protocol compliance, and conducting the safety reviews at the specified frequency, which must be conducted at a minimum of every 6 months (including when reapproval of the protocol is sought). During the review process, the principal investigator (monitor) will evaluate whether the study should continue unchanged, require modification/amendment, continue or close to enrollment. The principal investigator, the HIC, the FDA, or the RSC, have the authority to stop or suspend the study or require modifications.

**2. The risks associated with the current study are deemed moderate for the following reasons:**

We view the risks associated with radiation exposure as greater than minimal.

We do not view the risks associated with alcohol administration as minimal.

Although we have assessed the proposed study as one of greater than minimal risk, the potential exists for anticipated and/or unanticipated adverse events, serious or otherwise, to occur since it is not possible to predict with certainty the absolute risk in any given individual or in advance of first-hand experience with the proposed study methods. Therefore, we provide a plan for monitoring the data and safety of the proposed study as follows:

**3. Attribution of Adverse Events:**

Adverse events will be monitored for each subject participating in the study and attributed to the study procedures / design by the principal investigator [name]. according to the following categories:

- a.) Definite: Adverse event is clearly related to investigational procedures(s)/agent(s).
- b.) Probable: Adverse event is likely related to investigational procedures(s)/agent(s).
- c.) Possible: Adverse event may be related to investigational procedures(s)/agent(s).
- d.) Unlikely: Adverse event is likely not to be related to the investigational procedures(s)/agent(s).
- e.) Unrelated: Adverse event is clearly not related to investigational procedures(s)/agent(s).

#### **4. Plan for Grading Adverse Events:**

The following scale will be used in grading the severity of adverse events noted during the study:

1. Mild adverse event
2. Moderate adverse event
3. Severe

#### **5. Plan for Determining Seriousness of Adverse Events:**

##### **Serious Adverse Events:**

In addition to grading the adverse event, the PI will determine whether the adverse event meets the criteria for a Serious Adverse Event (SAE). An adverse event is considered serious if it results in any of the following outcomes:

1. Death;
2. A life-threatening experience in-patient hospitalization or prolongation of existing hospitalization;
3. A persistent or significant disability or incapacity;
4. A congenital anomaly or birth defect; OR
5. Any other adverse event that, based upon appropriate medical judgment, may jeopardize the subject's health and may require medical or surgical intervention to prevent one of the other outcomes listed in this definition.

An adverse event may be graded as severe but still not meet the criteria for a Serious Adverse Event. Similarly, an adverse event may be graded as moderate but still meet the criteria for an SAE. It is important for the PI to consider the grade of the event as well as its "seriousness" when determining whether reporting to the IRB is necessary.

#### **6. Plan for reporting UPIRSOs (including Adverse Events) to the IRB**

The principal investigator will report the following types of events to the IRB:

Any incident, experience or outcome that meets ALL 3 of the following criteria:

Is unexpected (in terms of nature, specificity, severity, or frequency) given (a) the research procedures described in the protocol-related documents, such as the IRB-approved protocol and informed consent document and (b) the characteristics of the subject population being studied; AND

Is related or possibly related to participation in the research (*possibly related* means there is a reasonable possibility that the incident, experience, or outcome may have been caused by the procedures involved in the research); AND

Suggests that the research places subjects or others at greater risk of harm (including physical, psychological, economic, legal, or social harm) than was previously known or recognized.

Unanticipated Problems Involving Risks to Subjects or Others (UPIRSOs) may be medical or non-medical in nature, and include – but are not limited to – *serious, unexpected, and related adverse events* and *unanticipated adverse device effects*. **Please note** that adverse events are reportable to the IRB as UPIRSOs **only** if they meet all 3 criteria listed above.

These UPIRSOs/SAEs will be reported to the IRB in accordance with IRB Policy 710, using the appropriate forms found on the website. All related events involving risk but not meeting the *prompt* reporting requirements described in IRB Policy 710 should be reported to the IRB in summary form at the time of continuing review. If appropriate, such summary may be a simple brief statement that events have occurred at the expected frequency

and level of severity as previously documented. In lieu of a summary of external events, a current DSMB report can be submitted for research studies that are subject to oversight by a DSMB (or other monitoring entity that is monitoring the study on behalf of an industry sponsor).

**7. Plan for reporting adverse events:**

For the current study, the following individuals, funding, and/or regulatory agencies will be notified (choose those that apply):

- All Co-Investigators listed on the protocol.
- National Institutes of Health
- Yale University Radioactive Drug Research Committee (if applicable)
- Yale University Radiation Safety Committee (if applicable)

The principal investigator, [name], in collaboration with [name] will conduct a review of all adverse events upon completion of every study subject. The principal investigator will evaluate the frequency and severity of the adverse events and determine if modifications to the protocol or consent form are required.

d. For multi-site studies for which the Yale PI serves as the lead investigator: **N/A**

- i. How will adverse events and unanticipated problems involving risks to subjects or others be reported, reviewed and managed?
- ii. What provisions are in place for management of interim results?
- iii. What will the multi-site process be for protocol modifications?

d. For multi-site studies for which the Yale PI serves as the lead investigator:

- iv. How will adverse events and unanticipated problems involving risks to subjects or others be reported, reviewed and managed? *Write here*
- v. What provisions are in place for management of interim results? *Write here*
- vi. What will the multi-site process be for protocol modifications? *Write here*

**13. Statistical Considerations:** Describe the statistical analyses that support the study design.

Frequency distributions and descriptive statistics for all variables will be computed before conducting analyses. Should Shapiro-Wilk normality tests indicate non-normality for any continuous variable, we will compute necessary data transformations (e.g., logarithmic) before conducting analyses.

**AIMs 1 and 2:** To determine which radiotracer is most sensitive to alcohol's effects on glutamate, regional  $V_T$  values (estimated for each radiotracer) will be analyzed with a linear mixed model featuring scan state (baseline and post-alcohol) as within-subject fixed factors, and region as a within-subjects factor. We hypothesize that the model will identify a significant main effect of scan state. Planned post-hoc contrasts will examine regional differences in  $V_T$  by scan state.

Effect sizes of alcohol relative to baseline will also be estimated. These values will guide selection of the experimental protocol for Aim 3.

**AIM 3:** The primary outcome measure will be the alcohol-induced change in mGlu5 availability, estimated as  $\Delta V_T = (V_T(\text{Alcohol}) - V_T(\text{Baseline})) / V_T(\text{Baseline})$ . The value of  $\Delta V_T$  will then be used as the primary outcome measurement for subsequent analyses.

To test the hypotheses that glutamate responses to alcohol are lower in heavy drinkers compared to moderate drinkers, a linear mixed model featuring group (heavy alcohol use vs. moderate use) as a between-subject fixed factor and region as a within subjects factor will be constructed. The main effect of group will be examined to test the null hypothesis of no difference in  $\Delta V_T$  between study groups. The interaction term between the two factors will also be examined. Post-hoc linear contrasts will examine regional differences in radiotracer  $\Delta V_T$  between groups.

Exploratory analyses at the voxel level will be conducted for all aims using whole brain data and SPM12.

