Positron emission tomography (PET) imaging with radiotracers specific to the metabotropic glutamate receptor 5 (mGlu5), [F]FPEB and [C]ABP688, provide an established technique to measure glutamate release. Ketamine, which elicits glutamate release, robustly reduces radiotracer distribution volumes ( $V_T$ ) in human brain. **We propose to leverage this imaging technique to measure alcohol-induced glutamate release in people.** However, these radiotracers exhibit subtle differences in the mechanism by which glutamate reduces mGluR5 availability. Therefore, in **Aims 1 and 2** we will evaluate both radiotracers and compare their effects to determine the optimal experimental approach. Each Aim will recruit 10 moderate drinkers who do NOT meet DSM-5 criterion for alcohol use disorder. We will strive to recruit the same subjects to participate in both Aims 1 and 2 for a direct comparison between approaches. For each aim, two mGlu5 PET measurements with arterial blood sampling will be acquired. Scanning will begin immediately following alcohol administration that will achieve 60 mg/dL for at no more than one hour, timed to capture the window of peak glutamate levels. This alcohol dose is similar to doses eliciting glutamate release in rodents and dopamine release in people. Subjective alcohol effects will be evaluated with the Biphasic Alcohol Effects Scale at baseline and every 30 min after alcohol for 90 min. The study will administer alcohol as an oral alcohol challenge first, however if sufficient

glutamate release is not achieved orally, then they study will switch to IV alcohol as the challenge in subsequent testing. The collected data will be used to accomplish the following specific aims:

**In Aim 1 we will determine the sensitivity of the PET radioligand [F]FPEB to the glutamate response from a fixed-dose alcohol session.** [F]FPEB  $V_T$ , an index of the number of mGlu5 available for radioligand binding, will be estimated throughout the brain. We hypothesize that alcohol will significantly reduce [F]FPEB  $V_T$  in the prefrontal cortex and striatum compared to baseline, consistent with glutamate release. The prefrontal cortex and striatum are brain regions with reported alcohol-induced glutamate release in preclinical models.

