**In Aim 2 we will determine the sensitivity of the PET radioligand [C]ABP688 to the glutamate response from a fixed-dose alcohol session.** [C]ABP688  $V_T$ , an index of the number of mGlu5 available for radioligand binding, will be estimated throughout the brain. We hypothesize that alcohol will significantly reduce [C]ABP688  $V_T$  in the prefrontal cortex and striatum compared to baseline, consistent with glutamate release. The prefrontal cortex and striatum are brain regions with reported alcohol-induced glutamate release in preclinical models.

The route of alcohol administration has important effects on brain neurochemistry. While oral alcohol provides a more naturalistic route of administration, the effects of first pass metabolism and gut absorption result in slower acute brain effects, which neuroimaging studies are typically less sensitive to. Therefore, the research plan will first evaluate the glutamate response to acute oral alcohol. However, given the diminished sensitivity of neuroimaging to this route of administration, should no effects of oral alcohol on brain neurochemistry be detected, we then plan to test for sensitivity to i.v. alcohol to leverage the more potent acute effects. This question of route of administration is a critical question in the experimental paradigm optimization, and will be addressed in subaims 1A, 1B, and 2A, 2B, respectively, before continuing to Aim 3.

Based on the results of the first aims, we will identify an optimal experimental paradigm. Using this approach, we next will recruit 30 moderate drinkers and 30 people who meet DSM-5 criteria for alcohol use disorder. Subjects will self-report recent and lifetime drinking patterns. Alcohol-induced glutamate release will be measured with ONE of the experimental approaches identified above to accomplish the following aim:

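### The Aims 1 and 2 analysis is meant to find the more sensitive tracer, but it never estimates the between-tracer difference or its uncertainty

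*Combined protocol and SAP*

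**What the plan says.** Section 13 (Statistical Considerations, AIMs 1 and 2) gives the purpose: "To determine which radiotracer is most sensitive to alcohol's effects on glutamate". Section 1 (Statement of Purpose) likewise says "we will evaluate both radiotracers and compare their effects to determine the optimal experimental approach". Sections 1 and 4.1 add that the team will try to enrol the same people for both tracers so that the two can be compared directly.

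The analysis is one model: regional VT for each tracer "will be analyzed with a linear mixed model featuring scan state (baseline and post-alcohol) as within-subject fixed factors, and region as a within-subjects factor". Its stated expectation is "We hypothesize that the model will identify a significant main effect of scan state". The planned contrasts are regional differences by scan state. Then: "Effect sizes of alcohol relative to baseline will also be estimated", and "These values will guide selection of the experimental protocol for Aim 3". No interval for these effect sizes is mentioned.

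Route is dealt with in the design. Under section 4.1, each tracer starts with oral alcohol in at least five subjects. It may move to i.v. if the change in VT stays within test-retest variability (9-12% for FPEB, below 12% for ABP688). Section 1 assigns the route question to sub-aims 1A, 1B, 2A and 2B, to be settled before Aim 3. It also expects oral alcohol to be harder to detect, "given the diminished sensitivity of neuroimaging to this route of administration". Section 13 does not mention route.

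**The concern.** The question is comparative and the model is not. Fitted to each tracer separately, it tests each against no change. Fitted to both together without a tracer term, it averages over them. In neither case does it produce the difference between tracers, a standard error for it, or any gain from pairing.

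The choice has consequences: one approach is carried into Aim 3, with 30 moderate drinkers and 30 people with alcohol use disorder. At 10 subjects per tracer, two effect sizes can differ noticeably by chance, and without an interval the team cannot tell a real difference from noise.

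Pairing cannot be assumed either. The ceiling of 40 moderate drinkers in section 6 equals 10 + 10 + (30 - 10), the count with no shared subjects; full sharing would need 10 + 20 = 30. The analysis has to work at any degree of overlap.

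A route switch adds a further gap. Section 13 does not say how oral and i.v. scans would enter the tracer comparison.

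**Working it through.** The documents give no power, precision or sample-size calculation for Aims 1 and 2, so there is no figure to reproduce. The calculations below are illustrative.

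**Inputs.** From the documents: n = 10 per tracer (Breakdown of Aims 1-3) and test-retest variability of 9-12% (section 4.1; PET Data Acquisition and Analysis gives below 12%). Assumed: the SD of a subject's percent change is 9-15 points and equal for both tracers. This reads the 9-12% either as an SD or as a mean absolute difference, in which case 12 x sqrt(pi/2) = 15.0. Also assumed: a correlation rho of 0 to 0.5 between a subject's two tracer changes. The documents' figure for ABP688 is an upper bound, and smaller SDs would narrow everything below.

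**Ten shared subjects.** SE = SD x sqrt(2(1 - rho)/10). Half-width = t(0.975; 9) x SE = 2.262 x SE. The probability that the less sensitive tracer shows the larger mean change is Phi(-d/SE) for a true difference of d points.

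| SD | rho | SE | 95% half-width | Wrong pick, d = 3 | Wrong pick, d = 5 |
|---|---|---|---|---|---|
| 9 | 0.5 | 2.85 | 6.4 | 14.6% | 3.9% |
| 9 | 0 | 4.02 | 9.1 | 22.8% | 10.7% |
| 12 | 0.5 | 3.79 | 8.6 | 21.5% | 9.4% |
| 12 | 0 | 5.37 | 12.1 | 28.8% | 17.6% |
| 15 | 0.5 | 4.74 | 10.7 | 26.4% | 14.6% |
| 15 | 0 | 6.71 | 15.2 | 32.7% | 22.8% |

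**No shared subjects.** Half-width = t(0.975; 18) x SD x sqrt(2/10) = 2.101 x SD x 0.447, which is 8.5 at SD 9, 11.3 at SD 12 and 14.1 at SD 15.

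**What the contrast adds.** With complete pairs on one route, the estimated contrast is simply the difference between the two mean changes. It favours the same tracer as the effect sizes do and adds only the interval.

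**If only one tracer switches route.** This was simulated with the section 4.1 rule applied strictly: i.v. follows if the mean change in the first five oral subjects is below 12%. The switched tracer then has 5 oral and 5 i.v. subjects and the other has 10 oral.
- Two equally sensitive tracers, true change 8-12%: exactly one switches in 19-50% of runs. In those runs the oral-only contrast leans against the switched tracer by about 2-8 points, because the switch was triggered by a small oral change.
- The unswitched tracer truly 3 points better: pooling routes picks the wrong tracer in about 18-21% of such runs if i.v. adds 5 points, and in about 33-57% if it adds 10. The oral-only contrast is biased by about -1.6 to -7.2 points.

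**The case against.** The strongest reply is that this is an exploratory selection at n = 10. The difference between two effect sizes is already the point estimate of the contrast, and the plan says only that these values will guide the choice. An interval of 6-15 points either side will seldom overturn that choice. Most of this stands: on one route with complete pairs, only the interval is missing. But wide intervals are the reason to report them, since they show when the data do not separate the tracers.

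A second reply is that sensitivity is more than mean change. It also depends on each tracer's noise, and section 13 leaves the type of effect size undefined. This stands too: a contrast of means should not be the only criterion, and the equal-SD assumption above is a simplification.

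A third concerns route. A reader might infer that the plan ignores route, that it will pool routes, and that pooling would usually select the worse tracer unless a route term were added. The documents do not support this. Sections 1 and 4.1 handle route by design, and pooling is nowhere planned. A calculation that treats the mixed-route layout as fixed overstates the harm, because under section 4.1 that layout arises only after a small oral change. For the same reason a route term does not remove the bias: with no shared subjects, the route-adjusted tracer contrast in this layout is the oral-only contrast, which is itself biased.

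**Conclusion.** The point holds as an inexpensive improvement. The stated model does not answer the stated question, and the Aim 3 choice rests on effect sizes with no stated uncertainty. Under the assumed SDs and correlations, the missing interval would be about 6-15 points either side, and the less sensitive tracer would be chosen in 15-33% of runs at a true difference of 3 points or 4-23% at 5. Reporting the contrast does not lower those error rates on one route with complete pairs; it makes them visible.

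On route, the finding is limited to section 13, which does not say how oral and i.v. scans enter the tracer comparison. If only one tracer switches, no simple contrast is unbiased, and the report should say so.

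**What to change.** In section 13, on log VT or the percent change already defined for Aim 3:

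- Estimate the between-tracer difference in alcohol-induced change (tracer by scan state) with a 95% interval, overall and for frontal cortex and striatum.
- For complete pairs on one route, use a paired analysis of each subject's change. With partial overlap, use a mixed model on region-averaged change with a random subject effect and a small-sample degrees-of-freedom correction. In simulation with 5 shared subjects, Satterthwaite degrees of freedom gave 6.7-6.8% rejection at a nominal 5%, so the interval should be read as slightly too narrow.
- Report each tracer's SD of change or standardised effect beside its mean change.
- Base the Aim 3 choice on these estimates and intervals, not on whether each tracer is separately significant.
- Report oral and i.v. effects separately and do not pool them. If only one tracer switches, state that the pooled, oral-only and route-adjusted tracer contrasts are all biased, and give the direction of the oral-only bias.

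The route text also needs reconciling. Section 1 says that if sufficient "glutamate release is not achieved orally, then they study will switch to IV alcohol as the challenge in subsequent testing", which reads as a study-wide switch. Section 4.1 sets the switch separately for each tracer. The PET Scans text in section 4.4 describes only i.v. alcohol for both tracers.

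The cost is SAP wording and slightly more analysis, with no new data. The intervals will be wide, so only large tracer differences will be resolved.
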